#### Data Sources

In order to identify patients in the primary target population, Business Intelligence & Advanced Analytics (BIAA), working with Geisinger's Phenomics and Clinical Data Core (PACDC), will provide a list of patients (including patient identifiers such as Medical Record Number) that were assessed by the Medial and each patient's associated risks.

We will also obtain contact information (address, phone number, email address) to message participants in the primary target population from BIAA & PACDC.

After the intervention is complete, we will obtain experimental outcome data for all 3 population groups from BIAA & PACDC. This will include data on patient flu vaccination, diagnosis of flu, diagnosis of flu-like symptoms, presence of flu-associated complications, hospital visits, and emergency department visits. This data set will additionally include patient characteristics that will be useful as analysis covariates, such as: age, patient primary care provider, and flu-related behavior and outcomes during previous flu seasons.

## STUDY DATA DETAILS

Data Management Procedures and Confidentiality. All data will be electronic. Datasets with identifying information will only be stored on Geisinger-managed, password-protected computers of the data brokers ([name], [name], and [name]) for the purpose of linking datasets from different sources.

A limited data set containing dates of service and ZIP codes will be shared with any non-Geisinger collaborators (e.g., Additional Principal Investigator [name] and his team) under a Data Use Agreement in compliance with HIPAA's Privacy Rule, and using data security protocols reviewed and approved by the Geisinger Security Office, Privacy Office, and Information Technology department.

After all data have been linked in a de-identified, coded file and analyzed, the datasets with identifiable information and any codes needed to link the identifiable information will be deleted. After the de-identified data have been fully analyzed, the de-identified dataset will be shared along with publications from this study. The deidentified data will not be destroyed or removed after any prespecified period of time has elapsed. We intend to permanently and securely archive the deidentified dataset at a research repository such as Open Science Framework (OSF) in order

> to be consistent with the best practices for open and reproducible science, as well as our obligation to the public as NIA-funded researchers.

The only study team members who will have access to identifiable and protected health information will be the data brokers: [name], [name], and [name]. Our non-Geisinger collaborators will have access to a limited data set which includes de-identified data as well as dates of flu vaccination and diagnosis. The remaining investigators will have access to the de-identified, coded data during data analysis.

We will analyze the data using standard behavioral research analysis methods, including computing bivariate correlations, using generalized linear models, using non-parametric models for non-normally distributed data, and entering variables as independent predictors in regression models to attempt to predict desired outcomes.

## RESEARCH ACTIVITIES AT OTHER SITES

Geisinger is the lead research team for this multi-site, single IRB study. Massachusetts Institute of Technology (MIT) and National Bureau of Economic Research (NBER) will cede to Geisinger's IRB. Research activities conducted at MIT and NBER will be limited to data analysis, using limited data and de-identified data, as described above. MIT and NBER will not be involved in study recruitment/enrollment or intervention administration.

Encouraging Flu Vaccination Among High-Risk Patients Identified by a Machine-Learning Model of Flu Complication Risk

NCT04323137

January 8, 2021

Statistical Analysis Plan

Project Status

All intervention messages have been disseminated. Data collection is ongoing, but an interim data analysis step will be conducted to inform COVID-19 vaccination efforts.

Planned Analyses

Primary Analyses:

Question 1: Does informing patients that they are at high risk for flu complications (a) increase the likelihood that they will receive flu vaccine; and (b) decrease the likelihood that they receive diagnoses of flu and/or flu-like symptoms in the ensuing flu season?

Analysis 1: We will evaluate if patients who are informed about their risk status (patients who were randomized to "high risk" message groups 2, 3, or 4 in the Study Design) exhibit improved flu vaccination and diagnosis rates compared with patients who were not informed (randomized to the control condition, group 1). To assess this, we will employ a generalized linear model with a binary distribution and log-link function (i.e. a logistic regression).

Question 2: Does informing patients that their high-risk status was determined (a) by analyzing their medical records (group 3) vs. by no specified method (group 2); and (b) by an AI/ML algorithm analyzing their medical records (group 4) as opposed to via unspecified methods or human medical records analysis affect the likelihood that they receive the flu vaccine and/or diagnoses of flu and/or flu-like symptoms in the ensuing flu season?

Analysis 2: We will evaluate this using 3 logistic regression models, comparing patients in groups 2 and 3, 2 and 4, and 3 and 4. Reported p-values will be adjusted for family-wise error rate across the three comparisons using Holm's procedure.

For both analyses described above, we will first assess the intraclass correlation (ICC) for patient-visited PCPs and/or clinics; if the ICC is greater than 0.1, a mixed model will be used with this variable included as a random effect.

Question 3: Patients in each of the conditions were stratified based on whether they were in the top 3rd percentile of risk, or in the subsequent 3rd-10th percentile. Patients in the former group were always told they were in the "top 3%" of risk. Patients in the latter group were either told they were in the "top 10%" of risk or that they were at "high" risk. These different risk conditions will be used to ask whether a) patients with the same risk level are affected by a vague verbal ("high") vs. specific numeric ("top x%") risk framing and b) patients with the same numeric risk phrasing are differentially affected due to different specific risk levels (3% vs. 10%). Analysis 3: We will evaluate this using a single logistic regression model with "top 10%" condition dummy coded as the reference level. This will allow the contrasts of "top 10%" vs. "high" (for question 3a) and of "top 10%" vs. "top 3%" (for question 3b).

Secondary Analyses:

We will use the approaches in Analyses 1 and 2 to evaluate the impact of the intervention on the secondary outcome measures listed in the pre-registration.

Exploratory Analyses

Impact on timing of shot

This analysis will focus on the subgroup of patients who were vaccinated. We will employ linear regression models to compare the time it took to receive a flu shot for patients who were informed about their risk status with those in the control group (as in Analysis 1) and among the 3 risk status communication conditions (as in Analysis 2). Time will be specified as the number of days since the beginning of the intervention (September 21, 2020). If the distribution of the time variable is skewed so as to violate the assumptions of a linear regression, data will be log transformed or analyzed using a gamma model.

Impact of age

While older patients tend to be aware of their increased vulnerability, younger patients may be more surprised to learn of their high-risk status. We will therefore examine the differential response of patients above vs. below age 65 by introducing this age variable as moderator and assessing if it interacts with experimental group to affect vaccination behavior. We will also conduct this analysis using age as a continuous variable.

Impact of modality

Patients who received an intervention message (groups 2, 3, and 4) may have received communications via up to 3 modalities. We will employ logistic regression to evaluate the impact of modality on outcomes of interest, assessing pairwise comparisons of the following modality combinations: letter only, letter + myGeisinger, letter + SMS, or letter + myGeisinger + SMS. The small number of patients who did not experience one of these modality combinations will be excluded for this analysis.

Impact of risk level and framing

We will evaluate the impact of risk level (top 3rd percentile vs. remaining 3-10th percentile) as a moderator for Analysis 1 and risk framing ("top 3%", "top 10%", "high") as a moderator for Analysis 2, assessing if the moderators interact with experimental group to affect study outcomes. As described in Analysis 3, risk framing will be dummy coded with "top 10%" as the reference level.

Analysis Exclusion Criteria

A small number of deceased patients and patients who received the flu vaccination before the start of the intervention were unintentionally included in this study. These patients will be

excluded from all analyses. Another small population of patients' print letters were returned to sender; these patients will remain included in analyses but will be documented as having not been contacted through this modality. Finally, due to delays in intervention rollout, there were patients who were vaccinated prior to the start of the study (9/21/20). These patients will be excluded from all above analyses, as they were not intended to receive the intervention.

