- 2. Does informing patients that their high-risk status was determined (a) by analyzing their medical records (vs. by no specified method); and (b) by an AI/ML algorithm¹ analyzing their medical records (as opposed to via unspecified methods or human medical records analysis) affect the likelihood that they receive the flu vaccine and/or diagnoses of flu and/or flu-like symptoms in the ensuing flu season?

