## Our specific aims are:

- 1. Evaluate the effect on flu vaccination rates of informing health-system patients who are identified by an ML analysis of EHR data to be at high-risk for flu complications that they are at high risk with either (a) no additional explanation, (b) an explanation that this determination comes from an analysis of their medical records, and (c) the additional explanation that an AI or ML algorithm made this determination.
- 2. Evaluate the effects of the same three interventions on diagnoses of flu in the same patients.

.

<sup>1 The study will not necessarily use the terms "AI," "ML," or "algorithm" in the messages; instead, these messages will be designed to be readable and comprehensible by the patient audience while still including the key concepts that differentiate the interventions from one another.

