Because this intervention is timed to the 2020–21 flu season, the intervention period will begin ~9/1/20 and last for three months. During that period, all identified primary target population participants will be randomized and will receive 1–3 separate messages (content based on their assigned condition) in sequence via postal letter, SMS, and patient portal modalities, using all modalities available for each participant. Outcomes will be measured as of 5/31/21. Data extraction from the EHR, data cleaning, data analysis, and manuscript preparation will begin on or after 6/1/21 and will include data from not only the primary target population but also the two secondary populations.

> The primary study outcomes will be the rates of flu vaccination and flu diagnoses during the 2020–21 season (start of intervention through 5/31/21) by the primary target population. We will also measure secondary, exploratory outcomes: Rates of flu vaccination and diagnoses by fellow household members of targeted patients; rates of flu vaccination and diagnoses by non-targeted patients who were assigned a risk score that fell just below the cutoff of targeted patients; rates of flu complications and flu-like symptoms among targeted patients, household members, and those at sub-threshold risk; and rates of other relevant healthcare utilization outcomes such as ER visits and hospitalizations.

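### SAP contrast 3b cannot attribute a top-3% versus top-10% difference to risk level, because the number told is the baseline risk stratum and no controls are used; a lesser mismatch concerns flu-like symptoms

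*SAP*

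**What the plan says.** **Contrast 3b.** The SAP (Primary Analyses, Question 3) describes two risk strata within every condition, control included: the top 3rd percentile and the 3rd to 10th percentile. Messaged patients in the first were always told *top 3%*. Messaged patients in the second were told either *top 10%* or *high*. Question 3b asks whether "patients with the same numeric risk phrasing are differentially affected due to different specific risk levels (3% vs. 10"%). Analysis 3 is one logistic model with *top 10%* as the reference level, and 3b is its contrast with *top 3%*. It names no outcome, no stratum term, no covariate and no comparison with controls. Further on, under Impact of risk level and framing, an exploratory analysis uses the risk stratum as a moderator of informed versus control.

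**Outcomes.** The protocol (Detailed Study Procedures) states: "The primary study outcomes will be the rates of flu vaccination and flu diagnoses". Its list of secondary, exploratory outcomes includes "rates of flu complications and flu-like symptoms among targeted patients, household members, and those at sub-threshold risk". Specific aim 2 is to "Evaluate the effects of the same three interventions on diagnoses of flu in the same patients". The protocol's second research question, however, asks whether the explanations "affect the likelihood that they receive the flu vaccine and/or diagnoses of flu and/or flu-like symptoms in the ensuing flu season". SAP Question 1, a primary analysis, asks whether messages "decrease the likelihood that they receive diagnoses of flu and/or flu-like symptoms in the ensuing flu season", and SAP Question 2 repeats the and/or wording. Analysis 1 says only that informed patients may "exhibit improved flu vaccination and diagnosis rates compared with patients who were not informed". Secondary outcomes are left to the "secondary outcome measures listed in the pre-registration", which is not among the documents.

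**The concern.** The wording of 3b is causal: patients are affected, and the effect is due to the risk level. Patients were randomised to conditions, not to risk strata. A comparison of messaged patients across strata therefore sets people with higher predicted complication risk against people with lower predicted risk. Their usual vaccination uptake or illness rate may differ whatever they were told. Such a difference could be published, from an analysis labelled primary, as evidence that one stated number moves patients more than another.

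The outcome mismatch is smaller. The and/or wording could mean flu alone, flu and symptoms as two endpoints, or a composite. A result on symptoms could then be presented as primary although the protocol's outcome list makes it exploratory.

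**Working it through.** **1. What 3b estimates.** On the log-odds scale, let b3 and b10 be the usual level in the upper and lower stratum without a message. Let m3 be the effect of *top 3%* in the upper stratum and m10 the effect of *top 10%* in the lower.

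- Contrast 3b = (b3 + m3) − (b10 + m10) = (b3 − b10) + (m3 − m10).
- Same-stratum comparison = [(b3 + m3) − b3] − [(b10 + m10) − b10] = m3 − m10.

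Only the second is free of the baseline gap b3 − b10.

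**2. Whether a stratum term helps.** Take the columns (intercept, *top 3%*, *high*, upper stratum). The three messaged groups have rows (1,1,0,1), (1,0,0,0) and (1,0,1,0). The second and fourth columns are identical, so the rank is 3 of 4. Adding controls from both strata gives full rank (5 of 5) only if the strata are assumed to respond equally to a message. If they may respond differently, the rank is 5 of 6. So m3 − m10 can be estimated, but it cannot be split into the number told and the stratum's own responsiveness.

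**3. Size, by illustration.** From the documents: 56,000 patients in the primary target population and four conditions. Assumed: equal arms of 14,000, two-sided 5%, *top 10%* and *high* split evenly, 50% uptake, and 30% in the upper stratum (3/10, from the percentile bands).

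- Told *top 3%*: 42,000 × 0.30 = 12,600.
- Told *top 10%*: 42,000 × 0.70 / 2 = 14,700.
- Controls: 14,000 × 0.30 = 4,200 upper; 14,000 × 0.70 = 9,800 lower.

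At 50% uptake the variance of a group's log odds is 1/(n × 0.25) = 4/n.

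- SE of 3b = √(4/12,600 + 4/14,700) = √0.000590 = 0.0243.
- SE of the same-stratum interaction = √(0.000590 + 4/4,200 + 4/9,800) = √0.001950 = 0.0442.
- Ratio = 0.0442/0.0243 = 1.82.

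Chance that 3b is significant with no message effect (Φ(z − 1.96), other tail negligible):

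| Baseline gap | Log odds ratio | z | Chance |
|---|---|---|---|
| 0 | 0 | 0 | 5% |
| 1 point (51% v 50%) | ln(0.51/0.49) = 0.0400 | 1.65 | 38% |
| 2 points (52% v 50%) | ln(0.52/0.48) = 0.0800 | 3.30 | 91% |

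The odds ratios concerned are only 1.04 and 1.08. With the upper-stratum share varied from 20% to 50% and lower-stratum uptake from 30% to 60%, the same formula gives about 32–45% at 1 point and 85–96% at 2 points. The same-stratum interaction stays at about 5% whatever the gap, because the gap cancels (step 1).

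**4. Outcomes side by side.** Flu diagnosis alone: the protocol's primary-outcome sentence and specific aim 2. Flu and/or flu-like symptoms: the protocol's research questions and SAP Questions 1 and 2. Unqualified diagnosis: Analysis 1. The protocol is thus inconsistent with itself, and the SAP carries over the looser wording.

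**The case against.** **Risk level may simply mean the stratum.** The SAP uses the term that way in Question 3a and in its exploratory section. On that reading 3b compares strata given the same style of message. This has force against claiming that the SAP plainly means the number told. It does not rescue 3b: *affected* implies a response to a message, and a contrast without controls cannot show one on either reading.

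**The moderator analysis already covers it.** In part. It uses controls and removes the baseline gap. But it is exploratory, and it pools *top 10%* with *high* in the lower stratum, so it does not hold the numeric phrasing constant, which is the premise of 3b. A reader might infer that relabelling is enough and no further model is needed; that is not quite so.

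**Covariates could adjust.** The protocol (Data Sources) mentions age and flu-related behaviour in previous seasons. The SAP names none for Analysis 3, and adjustment would not make the comparison randomised.

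**The gaps are assumed.** True. The figures show how readily a sample of this size detects a small gap, not that one exists. The confounding itself needs no number.

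**The primary outcomes are in fact defined.** This stands. A reader might infer that nobody can tell what is primary, but the protocol's outcome sentence is explicit and aim 2 agrees with it. A reader might also infer that false positives must rise. At an assumed 5% per test with independent outcomes, one comparison tested on two outcomes has a chance of 1 − 0.95² = 9.75% of a false positive, and on three 1 − 0.95³ = 14.3%. The rise occurs only if symptoms are a separate third outcome. A composite replacing flu diagnosis leaves two, and the plan claims no error control across outcomes.

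**Conclusion.** The point on 3b holds. As written, a contrast labelled primary cannot support its causal wording, because the number told coincides completely with baseline stratum and no controls enter. Under the stated assumptions a 1-point baseline gap would make it significant about 38% of the time, and a 2-point gap about 91%, with no message effect. Whether such a gap exists cannot be known from the documents.

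A reader might extend the criticism to all of Analysis 3 or to the arm comparisons. The documents do not support that. Contrast 3a compares two wordings within one stratum, although the SAP does not say how wording was assigned there, and Analyses 1 and 2 compare randomised conditions.

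The mismatch on flu-like symptoms is real but lesser: loose wording in the questions against an explicit outcome list, with the pre-registration unavailable to confirm it.

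**What to change.** **For 3b**

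- Label the raw *top 10%* versus *top 3%* contrast a non-randomised comparison of risk strata, and remove the wording that attributes it to risk level.
- Base 3b on a stratum-by-message interaction: *top 3%* against top-3% controls, compared with *top 10%* against 3rd–10th percentile controls.
- Name the outcome for Analysis 3, and state how *top 10%* or *high* was assigned within the lower stratum, since the comparison with lower-stratum controls relies on it.
- State that the interaction shows a different effect by stratum and cannot separate the stated number from a different response by stratum.

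Cost: one small additional model on data already planned, since strata exist in the control condition. Precision falls. At 80% power in the base case, the detectable difference goes from 2.80 × 0.0243 × 0.25 = 1.7 points to 2.80 × 0.0442 × 0.25 = 3.1 points. The conclusion available from 3b is weaker.

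**For outcomes**

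- In the protocol's research questions and SAP Questions 1 and 2, replace the and/or wording with flu diagnosis. Say in Analysis 1 that diagnosis means flu diagnosis, and list flu-like symptoms as secondary, as in Detailed Study Procedures.
- Check the result against the pre-registration and reconcile any difference.

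Cost: wording only.

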### Exclusion Criteria:

• Same as primary target population

> **Recruitment and Enrollment.** All patients meeting the primary target population criteria will be enrolled into one of the 4 experimental conditions. Anticipated enrollment number for this primary target population is 56,000. Only patients from this primary target population will be contacted. However, health record data will be accessed to assess secondary outcomes for household members of this target population (expected N of 234,000) and for patients whose risk scores were calculated by Medial's ML algorithm and determined to fall just below the high-risk cutoff (expected N of 56,000). This brings the total planned enrollment to 346,000 participants.

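### Analyses 1 and 2 name no baseline covariate for flu vaccination, so the message comparisons forgo precision that prior-season vaccination could supply

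*SAP*

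**What the plan says.** The SAP (Primary Analyses) describes Analysis 1, groups 2-4 against control, as follows: "we will employ a generalized linear model with a binary distribution and log-link function (i.e. a logistic regression". For Analysis 2 it states: "We will evaluate this using 3 logistic regression models, comparing patients in groups 2 and 3, 2 and 4, and 3 and 4", with Holm's procedure across the three p-values. The only further term offered in either analysis is conditional: "if the ICC is greater than 0.1, a mixed model will be used with this variable included as a random effect". Age, risk level and risk framing appear elsewhere in the SAP, but as exploratory moderators or, for framing, as the subject of Analysis 3.

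The protocol (Data Sources) says that the outcome data set will hold patient characteristics "useful as analysis covariates, such as: age, patient primary care provider, and flu-related behavior and outcomes during previous flu seasons". Its Study Data Details section adds a general sentence about putting predictors into regression models, but ties no covariate to any analysis. The SAP does not take up the list.

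Vaccination is one of two primary outcomes (protocol, Detailed Study Procedures): "The primary study outcomes will be the rates of flu vaccination and flu diagnoses". Two further SAP statements bear on the point. Under Analysis Exclusion Criteria: "there were patients who were vaccinated prior to the start of the study (9/21/20). These patients will be excluded from all above analyses". Under Project Status: "an interim data analysis step will be conducted to inform COVID-19 vaccination efforts".

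**The concern.** Whether someone was vaccinated last season is plausibly a strong predictor of whether they are vaccinated this season. The trial apparently plans to hold that information, yet the primary models ignore it. A prognostic baseline covariate in a randomised comparison removes outcome variance unrelated to the message and so narrows the interval around the effect.

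This matters most in Analysis 2. All three messages tell patients that they are at high risk and differ only in how that was determined, so true differences may be small, and Holm makes the first test stricter. A null result there would be hard to interpret if the comparison was less precise than the data allowed.

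The covariate also has to be named before outcomes are examined by arm. The protocol's open list leaves room for a later choice, and the SAP already announces an interim analysis.

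**Working it through.** The documents contain no power or sample-size calculation, so there is no figure of the plan to reproduce.

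**Inputs from the documents.** Protocol, Recruitment and Enrollment: "Anticipated enrollment number for this primary target population is 56,000". There are four arms, and Holm is applied over three comparisons.

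**Assumptions not in the documents.** Equal allocation (56,000/4 = 14,000 per arm), two-sided familywise alpha 0.05 (0.05/3 = 0.0167 at the first Holm step), uptake p = 0.5, true difference 1.5 points. Let q be the share vaccinated the season before.

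**Step 1: variance explained.** For a binary covariate, R² = gap² × q(1−q) / (p(1−p)), where gap is the difference in uptake between those vaccinated and not vaccinated the season before.
- q = 0.5, uptake 65% against 35%: 0.30² × 0.25/0.25 = 0.09.
- q = 0.5, uptake 80% against 20%: 0.60² × 0.25/0.25 = 0.36.
- q = 0.8, the same two pairs (p = 0.59 and 0.68): 0.06 and 0.26.

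The range carried forward is 0.06 to 0.36.

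**Step 2: detectable difference and power.** SE = √[p(1−p)(1−R²)(1/n₁+1/n₂)]. The detectable difference at 80% power is (z₁₋α/₂ + 0.842) × SE, and power is Φ(0.015/SE − z₁₋α/₂). Unadjusted, Analysis 2 has SE = √(0.25 × 2/14,000) = 0.00598, so the detectable difference is (2.394 + 0.842) × 0.598 = 1.93 points. Analysis 1 compares 14,000 with 42,000 at alpha 0.05: SE = 0.00488, and (1.960 + 0.842) × 0.488 = 1.37 points.

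| R² | Analysis 2: detectable (points) | Analysis 2: power at 1.5 points | Analysis 1: detectable (points) | Analysis 1: power at 1.5 points |
|---|---|---|---|---|
| 0 (as planned) | 1.934 | 54.6% | 1.367 | 86.7% |
| 0.06 | 1.875 | 57.7% | 1.325 | 88.7% |
| 0.16 | 1.772 | 63.5% | 1.253 | 91.8% |
| 0.26 | 1.663 | 70.0% | 1.176 | 94.7% |
| 0.36 | 1.547 | 77.1% | 1.094 | 97.0% |

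In sample-size terms the gain is 1/(1−R²): about 6% more patients at R² 0.06 and 56% more at 0.36. At the later Holm steps, Analysis 2 power goes from 61% to 64-82% (alpha 0.025) and from 71% to 74-88% (alpha 0.05).

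**Step 3: the exclusion of patients vaccinated before 9/21/20.** The SAP does not give their number. Take the unfavourable case: q = 0.5 before exclusion, and every excluded patient is a prior vaccinee. Excluding a share x leaves 14,000(1−x) per arm, and uptake among the remaining prior vaccinees falls to (0.5u − x)/(0.5 − x), where u is their uptake before exclusion.
- x = 10%: 12,600 per arm, p = 0.444, uptake 56.25/35 or 75/20, R² 0.05 to 0.30. Detectable difference 2.03 to 1.98-1.69 points; power 50% to 52-68%.
- x = 20%: 11,200 per arm, p = 0.375, uptake 41.7/35 or 66.7/20, R² 0.00 to 0.22. Detectable difference 2.09 to 2.09-1.85 points; power 47% to 47-59%.

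**Step 4: missing history.** If 20% have no prior-season record and average uptake, R² becomes 0.8 × 0.09 = 0.07 to 0.8 × 0.36 = 0.29, and the detectable difference is 1.86 to 1.63 points.

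**Step 5: simulation check.** Trials were simulated with a logistic model and a standardised risk difference (4,000 per scenario, alpha 0.0167). With q = 0.5, the adjusted SE was 0.954 (65/35) and 0.800 (80/20) times the unadjusted SE, and rejection at 1.5 points rose from 53% to 58% and from 54% to 78%. Over all scenarios with no effect, rejection was 1.3-1.8% unadjusted and 1.5-1.7% adjusted (nominal 1.67%).

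**Step 6: scale.** The SE of the log odds ratio is √(2/(14,000v)), with v the within-stratum variance: 0.0239 unadjusted (v = 0.25), 0.0251 adjusted at 65/35 (v = 0.2275), 0.0299 at 80/20 (v = 0.16). It rises with adjustment. Power still improves because the conditional odds ratio moves further from 1 than its SE grows. The gain appears as a smaller SE only on the marginal scale.

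**The case against.** The strongest reply is that this is a preference about efficiency. An unadjusted comparison of randomised arms is a legitimate primary analysis, and 14,000 per arm is large. Every benefit figure rests on assumed inputs. The 1.5-point example also sits where power is most responsive: at 2.0 points, first-step power is 83% unadjusted and 86-96% adjusted; at 1.0 point it is 24% and 25-38%, inadequate either way. The first Holm step is the strictest. If one message differs from the other two by 1.5 points, full Holm gives about 58% per true comparison and 71% for at least one, unadjusted. Finally, the protocol does not name prior vaccination as a field, and arm-level data may already have been analysed.

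Much of this stands. The point is not about validity, the size of the gain is unknown, Analysis 1 benefits little, and availability of the field is an inference to confirm. None of it shows that adjustment would do harm: in the worst case examined, precision is essentially unchanged. Nor does the protocol's general sentence on predictors fill the gap, since it assigns no covariate to a primary analysis.

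**Conclusion.** The concern holds. Analyses 1 and 2 specify no baseline covariate, although the protocol plans to collect one that is probably prognostic for vaccination. The primary tests remain valid and unbiased. Under the stated assumptions, adjustment lifts first-step power in Analysis 2 by between 3 and 23 percentage points, and by between nothing and 12 if 20% of patients, all prior vaccinees, are excluded. Analysis 1 gains about 2 to 10 points from an already adequate level. No gain is claimed for flu diagnosis, or from adding age or risk level. This is an inexpensive improvement that should be made. Confidence in its size is only moderate, because uptake, the strength of the association, the completeness of vaccination history and the number excluded are all unknown.

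**What to change.** For the vaccination outcome in Analyses 1 and 2:
- Confirm that prior-season flu vaccination is in the extract, then prespecify logistic regression on arm and that variable, coded yes, no or no history. Age and risk level are optional.
- Report a standardised risk difference with a robust SE alongside the odds ratio, and state that the adjusted odds ratio is conditional on the covariate.
- Keep the unadjusted model as a sensitivity analysis.
- If the ICC rule triggers, carry the covariate into the mixed model and say how the standardised difference is obtained, for example with SEs clustered by PCP or clinic.
- Fix the covariate before outcomes are analysed by arm. If that has already happened, leave the unadjusted result primary and label the adjusted one supplementary.

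As an editorial correction, the link function in Analysis 1 should be given as logit, since the SAP itself calls the model a logistic regression.

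The cost is SAP wording and minor analysis work, plus one added data field if prior vaccination is not in the extract. The drawbacks are a missing-history category, a second effect measure to report, and a benefit that shrinks if the no-history group or the early-vaccination exclusion is large.
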